Active syndromic population surveillance (biweekly) with PCR testing of symptomatic individuals – 12 months	15393 individuals (2108 households) Possible cases reporting any respiratory sign or loss of smell or taste, with or without fever, selected for PCR testing. Initially, before widespread community transmission, pooled testing of possible cases; when >50 confirmed cases per week, switch to PCR testing of 1 in 10 possible cases (systematic selection - every 10th possible case)	
 
● COVID-19 disease incidence rate (symptomatic infections per person-month)
 
● COVID-19 related hospitalisation rate
 
● Case (disease) fatality risk (%)
 
● Risk factors for severe outcome/hospitalization
 
● Basic reproduction number
 
● Effective reproduction number
 
● Serial interval
 
● Proportion uptake of measures to prevent infection; barrier uptake
 
● Effectiveness of interventions
 

		
 
• COVID-19 incidence density maps
 
• COVID-19 likelihood ratios of clinical signs
 
• Brand-specific vaccine effectiveness against confirmed COVID-19 (disease)
 

Age-stratified sero-survey at 0, 3, 6, 12 months	2400 individuals/dried blood spot samples per round (800 per age group <18yo, 18-50 yo, >50yo) An age stratified sample of individuals will be selected (simple random sample in each age group)	
 
• SARS-CoV-2 infection annual attack rate (%)
 
• Infection fatality risk
 
• Proportion asymptomatic infections, by age group
 
• Risk factors for infection
 
• Association between antibody titers and reinfection
 
• Brand-specific total vaccine effectiveness against SARS-CoV-2 seroconversion
 
• Overall vaccine effectiveness against SARS-CoV-2 seroconversion
 

Repeated social mixing survey	the same 2400 individuals selected for the sero-survey (800 per age group <18yo, 18-50 yo, >50yo)	
 
• correlation between number of contacts, intensity of contacts and attack rate
 
• correlation between uptake of control measures and attack rate
 
• social contact matrices to be used to parametrize dynamic transmission models
 

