An **age-stratified random sample** of that population will be selected for the **repeated sero- and social mixing survey**. By age stratum (0-17 years; 18-50 years; >50 years) we randomly select 800 individuals (simple random sample per age stratum; 2400 in total) from the Polana Caniço HDSS population (regardless of infection or disease status or history), from whom during home visits dried blood spots will repeatedly be collected at 0, 3, 6 and 12 months, vaccination status against COVID-19 will be recorded, and who will be asked to respond to a social mixing questionnaire. A HDSS sampling frame of all individual participants in the HDSS with socio-demographic data and unique identifiers, is available, and will be used to select a simple random sample of individuals by age group.

When a member of a household with no prior widespread transmission (see exclusion criteria) tests SARS-CoV-2 positive, we will revisit the household twice for a household transmission investigation: as soon as possible after the result of the household index case (baseline), and once again one month after symptom onset of the household index case. An initial contact report form will be filled in as soon as possible, ideally within 24 hours, after laboratory confirmation of the primary case in the household. Respiratory and dried blood spot samples will be collected of everyone considered resident (as defined by the HDSS) in the household and who has been in contact with the SARS-CoV-2 positive individual, regardless of age and presence or absence of symptoms. Respiratory samples will be analysed by RT-PCR for SARS-CoV-2 to assess presence of virus and viral load. The dried blood spots for serology on the Luminex assay. Data will be collected on household exposures of contacts and vaccine receipt. Symptomatic household contacts will be tested whenever symptoms appear, as part of the population-based surveillance. This is planned for upto 100 household index cases.

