## 7. Statistical Analyses

### 7.1 Methods

All estimated transmission or clinical outcome indicators will be adjusted for the design effect, related to the selection of HDSS enumeration areas (clusters) within the source populations. Intraclass correlation coefficients can be deducted from previous studies in the HDSS. The results of the sero-survey and social mixing survey will additionally be adjusted for age-stratified sampling.

We will calculate a incidence rate of COVID-19 disease throughout one year, adjusting for the sensitivity of SARS-CoV-2 RT-PCR on nasal swabs by delay between symptom onset and testing. Using the longitudinal sero-survey data, determining the proportion of asymptomatics, we will be able to adjust the clinical incidence rate to a SARS-CoV-2 infection incidence rate, and determine the SARS-CoV-2 infection annual attack rate and the infection fatality risk by age group.

We will undertake three risk factor analyses: of SARS-CoV-2 infection, of COVID-19 disease (symptomatic infection), and of COVID-19 hospitalisation and death (severe disease). Using negative binomial regression, we will investigate the association with socio-demographic factors, clinical characteristics such as underlying medical conditions, and uptake of preventive measures. We also investigate the association between SARS-CoV-2 infection (from the sero-survey) and recent exposure, contact and mobility patterns (from the social mixing questionnaire).

We will assume everyone will be susceptible initially and basic and effective reproductive numbers ( $R_0$  and  $R_e$ ) will be calculated by the rate of change of incidence over successive serial intervals (time between onset of infection of index and onset of infection of infected).

We will use established methods (Cauchemez et al 2004; te Beest et al 2013) to estimate generation time distribution, ratio of transmissibility between symptomatic and asymptomatic cases, duration of

the infectious period, and the basic reproduction number, from the transmission data collected in households.

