We will derive brand-specific total vaccine effectiveness against infection and against disease, in respectively a case-cohort design and a cohort design. Total vaccine effectiveness is the protection of vaccinees due to direct effects and added protection of vaccinees owing to vaccination of their neighbors or contacts, while overall vaccine effectiveness considers protection of an entire population, irrespective of the vaccination status of its individual members, due to the combination of total protection and protection of non-vaccinees due to vaccination of their neighbors or contacts (Ali et al 2015). To derive total vaccine effectiveness against infection, we will compare the proportion of sero-survey participants who seroconverted in the past 3 months among vaccinated against the proportion in non-vaccinated, adjusting for age and sex and other confounders. To derive total vaccine effectiveness against disease, we will compare the odds of vaccination among symptomatic confirmed SARS-CoV-2 cases detected through the population-based surveillance with the odds of vaccination among sero-survey participants who did not seroconvert in the past 3 months, in a case-cohort design. We will also explore overall vaccine effectiveness against disease using regression models comparing housing blocks with different levels of vaccination coverage among sero-survey participants.

We will estimate the conventional data-based secondary attack rate, which is the proportion of seroconversion among identified household contacts. However, these are not necessarily all secondary infections from the household index case, and could be tertiary. Therefore we will also derive a model-based secondary attack rate, estimating the number of actual secondary infections of the household index case. To do so, we could use a chain-binomial statistical model, as described by Jing et al (doi:10.1016/S1473-3099(20)30471-0), with an expectation-maximisation algorithm to account for (a) uncertainty in the infection time of asymptomatic infections, for (b) an incubation and infectious period distribution, as described in literature, and consider (c) the timing of symptom onset in

symptomatic household contacts and (d) the age-specific proportion of asymptomatic infections as estimated from the active population-based surveillance and sero-survey.

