## 7.2 Sample size and power

Assuming a 40% annual attack rate, 50% symptomatic infections (cases), 2% overall case fatality risk, of which 90% are identified by the active population surveillance, 2790 COVID-19 cases and 56 deaths will be identified through the study period. The average incidence rate of the HDSS population would then be 1.50 cases per 100 person months with lower and upper 95% confidence interval limits 1.45 and 1.56. The overall case fatality risk would have as lower and upper 95% confidence interval limits at 1.53 and 2.58%.

To determine the infection attack rate from a simple random population sample of three age strata (comparable in size), with +/-3% confidence limits, 95% confidence interval, assuming the attack rate may reach 40% towards the end of the study period, samples from 800 individuals per age stratum per round will need to be collected.

Assuming the household secondary attack rate to be close to 17% (Fung et al, Clin Infect Dis, 2020) and a median household size of 7.3 (based on HDSS data), a 5% confidence limit and a design effect of 3, 642 household members will need to be enrolled, or 100 households. The WHO also recommended to include 100 households in household transmission investigations.

Assuming 20% vaccination coverage among the 2400 sero-survey participants, 5% of sero-conversion over 3 months and 10% of seroconversion over 6 months, a 95% two-sided confidence interval and an anticipated crude total vaccine effectiveness of 50%, there will be 66% power to observe this effect after 3 months and 97% power after 6 months.

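### The household analysis does not separate the symptomatic, surveillance-detected index from the true primary case, and does not condition on how households are found

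*Combined protocol and SAP*

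**What the plan says.** **How index cases are found.** Table 1 (section 2) limits surveillance PCR: "Possible cases reporting any respiratory sign or loss of smell or taste, with or without fever, selected for PCR testing". The footnote to Table 5 says the same, and the four entry points in section 4.2 all lead to people with symptoms or suspected disease.

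**What the index is called.** Section 4.2 asks for the first contact form "after laboratory confirmation of the primary case in the household". Table 4 uses *primary case* and *index case* for the same person. Section 4.3 excludes only households with more than three known positives in 7 days, so up to three may be known at entry. No rule says who was first.

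**What is estimated.** Section 7.1 defines a conventional secondary attack rate, "which is the proportion of seroconversion among identified household contacts". It notes that "these are not necessarily all secondary infections from the household index case, and could be tertiary" and then states: "Therefore we will also derive a model-based secondary attack rate, estimating the number of actual secondary infections of the household index case". A chain-binomial model is offered as one that could be used, allowing among other things for "uncertainty in the infection time of asymptomatic infections". Separately, section 7.1 assigns the "ratio of transmissibility between symptomatic and asymptomatic cases" to two other published household methods.

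**What is collected.** All resident contacts have a swab and a dried blood spot on Day X+1 and day 28, with or without symptoms. The index has blood on both days and a second swab on day 28 (section 4.2, Table 3).

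**The concern.** Suppose A is infected first without symptoms and infects B, who becomes ill and is swabbed. B is the index. If B is also taken as the start of the chain, A's infection is charged to B, as are any others that A caused. Had A infected nobody who became ill, the household would not have been found. Symptomatic primaries therefore enter whether or not they transmitted, and asymptomatic primaries mainly when they did.

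The household secondary infection rate and the role of asymptomatic infection in transmission are both primary objectives. Section 7.1 feeds household estimates into the population model. Viral load and symptoms of the index are planned predictors of household infection; where the index is not the source, they describe the wrong person.

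**Working it through.** **1. The plan's own figure.** Section 7.2 asks for 642 household members (17% attack rate, ±5 points, design effect 3). With a finite population correction for N = 15,393:

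n = 3 × N × p(1−p) / [(0.05²/1.96²)(N−1) + p(1−p)], p = 0.17
= 6,515.9 / (10.017 + 0.141) = 641.5, so 642.

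This reproduces. The documents give no figure for how often the index is not the primary, so the rest is conditional on assumptions.

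**2. Inputs.**
- Asymptomatic share a: 50% (section 7.2); 20-50% (section 1.1).
- Contacts: 7.3 − 1 = 6.3 (section 7.2); Table 1 uses 6.
- Detection of symptomatic cases: 90% (section 7.2).
- Per-contact risk q: assumed 0.10 or 0.17. If the 17% in section 7.2 is the conventional rate, which includes later generations, q is nearer 0.10: simulated with r = 1, 0.10 gives a final rate of 16.2% and 0.17 gives 34.6%.
- Infectiousness of asymptomatic relative to symptomatic cases, r: not given; assumed 1 or 0.5.

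**3. Asymptomatic primaries alone.** Such a household enters if the primary directly infects someone who becomes ill:

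e = 1 − [1 − q·r·(1−a)]^6.3; share = a·e / [(1−a) + a·e].

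With a = 0.5, q = 0.17, r = 1: e = 1 − 0.915^6.3 = 0.429; share = 0.214/0.714 = 30%.

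**4. All routes.** A household simulation (size 7-8, 90% detection, assumed generation time mean 5 days, incubation mean 5.5 days, detection delay 0-7 days) adds longer chains, missed symptomatic primaries and detection out of order.

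| Asymptomatic | q | r | Step 3 | All routes |
|---|---|---|---|---|
| 50% | 0.10 | 0.5 | 13% | 20% |
| 50% | 0.10 | 1 | 22% | 31% |
| 50% | 0.17 | 0.5 | 19% | 32% |
| 50% | 0.17 | 1 | 30% | 44% |
| 20% | 0.10 | 0.5 | 5% | 16% |
| 20% | 0.10 | 1 | 9% | 20% |
| 20% | 0.17 | 0.5 | 8% | 23% |
| 20% | 0.17 | 1 | 13% | 28% |

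Runs with 6 contacts and shorter intervals (means 4 and 5 days) move entries by a few points, giving about 20-43% and 14-28%. With 1-in-10 testing, and asymptomatic shares of 20% to 56%, the simulation gives 38-67%. The documents do not say whether the first 100 households will be complete before that switch.

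**5. Secondary attack rate.** About 3-12% of contacts were infected before the index: of 600 contacts, 0.03 × 600 = 18 to 0.12 × 600 = 72. With a = 0.5 and r = 1, the proportion of contacts infected in enrolled versus all infected households was 22.7% vs 16.2% (q = 0.10) and 43.5% vs 34.6% (q = 0.17). The gaps of 6.5 and 8.9 points exceed the planned ±5. For the conventional rate, a contact infected before the index but still seronegative at X+1 is counted as secondary. One already seropositive cannot seroconvert but, with no stated rule, may stay in the denominator and pull the rate down.

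**6. Transmissibility ratio.** The direction depends on the analysis.
- Index forced to be primary (two-type Reed-Frost final-size fit, 6 contacts, q = 0.17, a = 0.5): symptomatic/asymptomatic = 0.216/0.144 = 1.5 when the truth is 1.0, and 0.195/0.073 = 2.7 when the truth is 2.0. Asymptomatic transmission is understated.
- True primary identified, ascertainment ignored: asymptomatic/symptomatic first-generation attack is about 2.1-2.2 (q = 0.10) or 1.5 (q = 0.17) when the truth is 1.0. Asymptomatic transmission is overstated.

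**The case against.** The best defence is that no analysis text fixes the index as the primary. The equation of the two rests on loose wording in section 4.2 and Table 4; the analysis text says *index*. Allowing for uncertain infection times of asymptomatic members does not bar a time before the index's onset. The transmissibility ratio is assigned to other methods, one of them titled a Bayesian MCMC approach for household longitudinal data, which may leave the first infection unknown. The documents alone do not settle that.

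A reader might also infer that nobody without symptoms is swabbed. That holds only for finding the index; all contacts are swabbed and bled twice, so information on earlier infection will exist.

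Nor is antibody positivity at X+1 a clean marker of an earlier household infection. It may reflect old infection or vaccination, since the assay includes spike. With 6 independent contacts, at least one is seropositive in 1 − 0.962^6 = 21% of households at the 3.8% seroprevalence in section 1.2, and in 1 − 0.6^6 = 95% at a 40% attack rate.

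These points narrow the concern but do not remove it. The stated target is still infections of the index, the model is optional, and nothing commits the analysis to using the X+1 data in this way or to conditioning on ascertainment.

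**Conclusion.** The gap is real and bears on two primary objectives. At the plan's 50% symptomatic and 90% detection, with q of 0.10-0.17 and r of 0.5-1, the index is not the primary in about 20-43% of enrolled households; with 20% asymptomatic, about 14-28%. If 17% is the conventional rate, the q = 0.10 rows are the more relevant. Charging earlier infections to the index inflates the secondary attack rate by an amount that can exceed the planned precision.

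Three stronger readings are not supported. The plan does not state that the first positive is analysed as the primary, so the estimates are exposed to bias rather than certain to be wrong. No single percentage can be attributed to the documents, because q and r are assumed. And the transmissibility ratio cannot be said to lean one way: its direction depends on which of the two corrections is omitted.

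**What to change.** In section 7.1:

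1. Define index (triggers the investigation), primary (first infected) and co-primary cases separately, and use the terms consistently in section 4.2 and Table 4.
2. For the model-based secondary attack rate, and for the household methods used for the transmissibility ratio, treat the primary as unknown among infected members, index included. Use onset dates and the Day X+1 and day 28 PCR and serology.
3. Condition the likelihood on the household being found through a detected symptomatic case. Steps 2 and 3 are needed together, since either alone leaves the ratio biased.
4. For the conventional rate, exclude from the numerator contacts with evidence of infection before the index, and remove contacts already seropositive at X+1 from the at-risk denominator.
5. Add a sensitivity analysis restricted to households in which no contact has evidence of recent infection before the index (earlier onset, or PCR positivity at X+1). Do not count antibody positivity alone.

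The cost is more modelling work and wider intervals, without new samples. Where X falls late, rules 4 and 5 also drop some contacts or households that the index had already infected by X+1. The restricted estimate should therefore be read as a check beside the main model, not as a replacement.

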## 7.2 Sample size and power

Assuming a 40% annual attack rate, 50% symptomatic infections (cases), 2% overall case fatality risk, of which 90% are identified by the active population surveillance, 2790 COVID-19 cases and 56 deaths will be identified through the study period. The average incidence rate of the HDSS population would then be 1.50 cases per 100 person months with lower and upper 95% confidence interval limits 1.45 and 1.56. The overall case fatality risk would have as lower and upper 95% confidence interval limits at 1.53 and 2.58%.

To determine the infection attack rate from a simple random population sample of three age strata (comparable in size), with +/-3% confidence limits, 95% confidence interval, assuming the attack rate may reach 40% towards the end of the study period, samples from 800 individuals per age stratum per round will need to be collected.

Assuming the household secondary attack rate to be close to 17% (Fung et al, Clin Infect Dis, 2020) and a median household size of 7.3 (based on HDSS data), a 5% confidence limit and a design effect of 3, 642 household members will need to be enrolled, or 100 households. The WHO also recommended to include 100 households in household transmission investigations.

Assuming 20% vaccination coverage among the 2400 sero-survey participants, 5% of sero-conversion over 3 months and 10% of seroconversion over 6 months, a 95% two-sided confidence interval and an anticipated crude total vaccine effectiveness of 50%, there will be 66% power to observe this effect after 3 months and 97% power after 6 months.

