All HDSS households will be visited by a trained HDSS interviewer to present the study and ask for informed consent (i) by the household head for the population-based surveillance and (ii) by the individuals selected for the age-stratified serial sero-survey. During this same visit, if the household head consented, the demographics data (baseline household visit form) will be verified and updated. A study household card with unique IDs of each household member will be provided (code containing the housing block, household id and sequential household member number). Household members will be sensitized on symptoms related to COVID-19, are asked to keep track of possible symptoms they may develop, and inform the study team by phone if a household member has a respiratory symptom, loss of smell or taste, so that upon assessment he/she can be asked to be swabbed for virological testing. In case a household member presents with symptoms which classify him/her as a possible case, a separate individual informed consent procedure for nasal swabbing will have to be performed prior to sampling. This ICF covers sampling for the first episode and any subsequent episode during the study period when nasal sampling would be indicated. Also during the baseline household visit, if full informed consent was provided (both for surveillance by the household head and for the sero- and social mixing survey by the individual household member), individual household members selected for the sero-survey will be asked for a baseline dried blood spot sample on filter paper, by administering a few blood drops through a finger prick.

Every two weeks a trained interviewer from the HDSS team will do calls to the head of the household or his representative, where during the call he will fill out a questionnaire (Household follow-up visit form) recording any respiratory symptoms, fever or other indicative sign of COVID-19 (at the time of the phone call, or in the last two weeks, if these symptoms go away), vaccination against COVID-19, and medical appointments that any family member has had.

Meanwhile (if applicable), demographic changes or changes in the chronic medical conditions of family members will be recorded. If a family member reports a respiratory sign or loss of smell or taste, with or without fever (possible case), a trained interviewer will do a home visit to this household.

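### Section 7.2 labels a detected rate of 1.50 as the HDSS population's incidence when its inputs imply 1.67, and section 7.1 has no correction for symptomatic cases not found or not tested

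*Combined protocol and SAP*

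**What the plan says.** Section 7.2 starts from a 40% annual attack rate and half of infections symptomatic, and continues: "of which 90% are identified by the active population surveillance, 2790 COVID-19 cases and 56 deaths will be identified". It then concludes: "The average incidence rate of the HDSS population would then be 1.50 cases per 100 person months", with 95% limits of 1.45 and 1.56.

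Table 1 marks COVID-19 disease incidence in bold as a primary outcome and defines it as symptomatic infections per person-month. The definition is not restricted to detected infections.

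For the analysis, section 7.1 calculates disease incidence "adjusting for the sensitivity of SARS-CoV-2 RT-PCR on nasal swabs by delay between symptom onset and testing". It also adjusts all indicators for the design effect, and it uses the asymptomatic proportion from the sero-survey to turn the disease rate into an infection rate.

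A person with symptoms must be reported or present, must agree to be swabbed and must be tested before being counted. On the second step, section 5.1 says that "a separate individual informed consent procedure for nasal swabbing will have to be performed prior to sampling". On the third, Tables 1 and 4 provide for PCR testing of only every tenth possible case once confirmed cases exceed 50 in a week.

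**The concern.** Two things do not fit together. First, the planning figure for a primary outcome carries the label of one quantity (the rate in the population) and the value of another (the rate among cases that surveillance picks up). Second, the analysis section does not bridge the two. A correction for PCR sensitivity can act only on people who were swabbed and tested. The design-effect adjustment concerns variance. The asymptomatic proportion converts disease incidence to infection incidence and leaves the disease rate as it was. No section describes an adjustment for symptomatic people who were not found, declined the swab or were not selected for testing.

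At stake is the burden figure itself. Section 10.2 has the incidence rate presented to health authorities and the national response team after 3, 6 and 12 months. An analyst who follows section 7.1 literally would report a rate that is biased downwards, with an interval that does not reflect the missing part.

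**Working it through.** **Inputs.** Section 7.2: attack rate 0.40, symptomatic 0.50, identified 0.90, 2,790 identified cases, rate 1.50 (1.45 to 1.56). Section 4.1: population 15,393. Synopsis: 12 months. Tables 1 and 4: 1-in-10 testing above 50 confirmed cases per week.

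**1. Reproducing the plan's figures.** Identified cases = N × 0.40 × 0.50 × 0.90.
- N = 15,393 gives 2,770.7.
- N = 15,500 gives exactly 2,790, over 15,500 × 12 = 186,000 person-months.
- Rate = 2,790 / 186,000 × 100 = 1.50. It is 1.50 with either N.
- The Poisson 95% interval is 1.445 to 1.557 (exact and log-scale agree to three decimals), which matches the stated limits to within 0.01.

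**2. The population rate from the same inputs.** Dropping the 0.90: 0.40 × 0.50 / 12 × 100 = 1.667 per 100 person-months. With 3,100 cases over 186,000 person-months the exact Poisson interval is 1.61 to 1.73. Since 1.667 × 0.90 = 1.50, the printed figure is the detected rate, 10% below the implied population rate.

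**3. What remains after the section 7.1 correction.** This depends on what the 90% covers, which the documents do not say.
- Case-finding only: the PCR correction restores false negatives but not missed people. The corrected rate is 1.667 × 0.90 = 1.50, or 10% low.
- Case-finding and PCR error combined: with sensitivity s, the part not due to PCR is 0.90 / s, and the corrected rate is 1.667 × 0.90 / s. The documents give no s, so a range is assumed:

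| Assumed PCR sensitivity | 0.90 / s | Corrected rate | Residual |
|---|---|---|---|
| 0.90 | 1.000 | 1.67 | 0% |
| 0.95 | 0.947 | 1.58 | −5.3% |
| 0.98 | 0.918 | 1.53 | −8.2% |
| 1.00 | 0.900 | 1.50 | −10% |

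On this factor the residual therefore lies between 0 and −10%.

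**4. The 1-in-10 phase.** The expected 2,790 cases average 2,790 / 52 = 53.7 per week, already above the trigger, so the plan's own assumptions make the switch likely. If a share f of detectable cases falls in that phase and results are counted without weights, the rate becomes 1.50 × (1 − 0.9f). The documents do not give f. For assumed values of 10%, 25% and 50% the rate is 1.365, 1.163 and 0.825. Even a modest share costs about as much as the whole 90% factor, and a large share costs several times more.

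**5. The proposed sensitivity range on the planning figures.** Detected rate divided by case detection: 1.50 / 1.00 = 1.50, 1.50 / 0.90 = 1.67, 1.50 / 0.80 = 1.88.

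**The case against.** The strongest reply is that 1.50 is a planning illustration, not the estimator. Surveillance covers the whole HDSS, no sample size depends on the figure, and relative precision is nearly the same at 1.67. That is right, and it limits what can be claimed. A reader might infer that the study's reported 95% interval will exclude the true rate. The documents do not support that: 1.45 to 1.56 is a pre-study Poisson interval for the detected rate, and the final analysis also adjusts for the design effect. What stands is the wrong label in section 7.2 and the missing correction in section 7.1.

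A reader might also infer that the primary estimate is expected to be 10% low. That needs the 90% to mean case-finding alone. A case counts as a confirmed COVID-19 case only after swab consent and a positive PCR, so the 90% may be an end-to-end figure, and section 7.1 would then recover part or all of the gap. Full recovery requires that the entire loss is PCR error, with complete case-finding and no refusal.

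Other tempting extensions also fail:
- Adding swab refusal of 10 to 30% on top of the 90%, to reach 1.35 to 1.05, rests on assumed rates. The only refusal figure in the plan (10%, section 5.2) is for the finger-prick sero-survey, and the 90% may already include refusal.
- The gap between 2,790 and 2,771 cases is 0.7%, against a population that the synopsis calls approximate. It is not a material error.
- The plan does mitigate missed cases, through four entry points for detection, fortnightly calls, three-monthly visits and weekly data-quality reports. These reduce losses but do not correct the estimate for those that remain.

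Finally, the sero-survey might be thought to settle the matter. If missed symptomatic seroconverters are classed as asymptomatic, the symptomatic share falls from 0.50 to 0.50 × 0.90 = 0.45, and 1.50 / 0.45 = 3.33, which equals 0.40 / 12 × 100. The infection rate would come out right, but the disease rate would still be 1.50.

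**Conclusion.** The point holds in this form. The 1.50 (1.45 to 1.56) in section 7.2 is a detected rate under a population label; the same inputs give 1.67 (1.61 to 1.73). Section 7.1 corrects the primary disease incidence for PCR sensitivity but not for symptomatic people never found, not consenting to the swab or not selected in the 1-in-10 phase. On the 90% assumption alone the estimate would be between 0 and 10% low, with the full 10% only if the 90% is case-finding alone. An unweighted 1-in-10 phase could add a much larger shortfall, of a size set by how many cases fall in it, which the documents do not allow one to predict. The arithmetic is certain. The residual bias is conditional on the undefined 90%, on an assumed PCR sensitivity, and on section 7.1 being followed as written.

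**What to change.** In section 7.2, label 1.50 as the detected rate, give 1.67 as the implied population rate, and say whether the 90% covers case-finding only or also swab refusal and PCR error.

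In section 7.1, weight PCR results by the inverse of the proportion of possible cases actually tested within week and age group. One set of weights then covers both refusal and 1-in-10 selection. It assumes that untested possible cases have the same positivity as tested ones in the same week and age group, and that should be stated. Then report incidence at 90% case detection with a sensitivity range of 80 to 100%. The divisor must be case-finding only, so that refusal and PCR error are not corrected twice.

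Do not estimate the detection proportion from the sero-survey panel unless symptom history is collected there independently of the surveillance. As described, symptoms are captured through the same surveillance channels, so a missed symptomatic person would be classed as asymptomatic and the ratio would be pushed towards 100%.

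The cost is some wording, a little more analysis and a wider reported interval, mainly from the weights in the 1-in-10 phase. No new data are needed beyond a count of possible cases and of those tested by week and age group.
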